7.6.6 PK/PD

C_{trough} values will be summarized at Weeks 2, 4, 6, and 11. C_{p2hr} values will be summarized on Day 1, using descriptive statistics by treatment group.

[REDACTED]

7.7 Safety

7.7.1 Extent of Exposure

Duration of exposure to study drug in the double-blind Treatment Period will be defined as the total number of days of administration of the study drug, regardless of unplanned intermittent discontinuations:

(Date of last dose of double-blind study drug taken – date of first dose of double-blind study drug taken) + 1

Duration of exposure to study drug (days) in the double-blind Treatment Period will be summarized using descriptive statistics for each treatment group and overall for the Safety population.

The number and percentage of patients randomized and exposed to the study drug will also be presented by double-blinded treatment duration categories for each treatment group and overall for the Safety population:

- <7 days
- ≥7 and <14 days
- ≥14 and <21 days
- ≥21 and <28 days
- ≥28 and <35 days
- ≥35 and <42 days
- ≥42 days

7.7.2 Adverse Events

All AEs recorded on the eCRF will be coded using the MedDRA dictionary (Version 23 [or a later version if updated during the study]) and classified as TEAEs as follows:

- TEAEs are events with start date and time on or after the date and time of first dose of study drug during the double-blind Treatment Period or single-blind Safety Follow-up Period, or events with start date and time prior to the date and time of first dose of study drug during the double-blind Treatment Period whose severity worsens on or after the date and time of first dose of study drug during the double-blind Treatment Period or single-blind Safety Follow-up Period.

All AE data will be listed by treatment group with TEAE status flagged in the listing. In addition, listings of treatment-emergent SAEs, TEAEs leading to discontinuation of study drug during the double-blind Treatment Period and TEAEs resulting in death will be produced.

Summary tables of TEAEs by treatment group and overall will be produced for the double-blind Treatment Period and the single-blind Safety Follow-up Period for the Safety population.

The relationship between an AE and study drug is assessed as definite, probable, possible, unlikely, or not related. A drug-related AE is an AE considered by the investigator as definitely, possibly, or probably related to study drug or with unknown/missing relationship to study drug.

An overview table will summarize the number and percentage of patients with at least 1 of the following TEAEs, where patients with more than 1 TEAE in a particular category are counted only once in that category:

- Any TEAE
- Drug-related TEAE
- Severe drug-related TEAE
- Treatment-emergent SAEs
- Drug-related treatment-emergent SAEs
- TEAE leading to study drug discontinuation
- Drug-related TEAE leading to study drug discontinuation
- TEAE leading to death

The number and percentage of patients reporting each AE will be summarized by SOC and PT for the Safety population. Tables will be sorted alphabetically by SOC. Preferred terms will be sorted by descending overall total. The following summaries will be produced:

- TEAEs by SOC and PT
- TEAEs by PT
- TEAEs reported by at least 5% of patients in any treatment group, by SOC and PT
- TEAEs related to study drug, by SOC and PT
- TEAEs related to study drug, by PT
- TEAEs by relationship (related, or unrelated) to study drug, by SOC and PT
- TEAEs by severity, by SOC and PT
- TEAEs related to study drug by severity, by SOC and PT
- TEAEs causing discontinuation from study drug, by SOC and PT
- TEAEs related to study drug causing discontinuation from study drug, by SOC and PT
- Treatment-emergent SAEs, by SOC and PT
- Treatment-emergent SAEs related to study drug, by SOC and PT
- TEAEs leading to death, by SOC and PT
- SAEs during Screening or Run-in Periods leading to death, by SOC and PT
- The five Specific TEAEs and time to onset, by PT
- The five Specific TEAEs and AE duration, by PT
- The five Specific TEAEs and PHN drug use, by PT
- The five Specific TEAEs and age category (<50, 50-65, 66-75, and >75 years old), by PT
- The five Specific TEAEs and sex, by PT
- The five Specific TEAEs and race, by PT
- The five Specific TEAEs and country, by PT

In the above summaries, patients with more than 1 AE within a particular SOC are counted only once for that SOC. Similarly, patients with more than 1 AE within a particular PT are counted only once for that PT. For summaries by severity, patients with multiple AEs within a particular SOC or PT will be counted under the category of their most severe AE within that SOC or PT. In a similar manner, summaries prepared by drug relationship will select the event with the greatest degree of relationship when a patient reports multiple occurrences of the same event.

The 5 specific TEAEs are defined in [Section 7.6.4](#). For the summary of the 5 specific AEs by time to onset and AE duration, the denominator for percentage is defined as the number of patients in each subgroup with the respective specific TEAEs in the double-blind treatment period for each treatment group. For the other subgroups,

the denominator for the percentage is defined as the number of patients in each category of a subgroup in each treatment group.

The number and percentage of patients with drug interruption due to AE in the double-blind treatment period will be summarized by treatment group for the Safety population.

No statistical comparisons of AEs between treatment groups will be performed.

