9.1.2 Serious Adverse Events

All SAEs will be collected starting with signing informed consent and continue until 35 days after the last dose of study drug.

An SAE is defined as any AE that results in any of the following outcomes:

- Death;
- A life-threatening AE - defined as an event, in the view of the Investigator, the occurrence of which places the patient or patient at immediate risk of death. It does not include an AE that, had it occurred in a more severe form, might have caused death;
- Hospitalization or prolonging of an existing hospitalization;

- A persistent or significant incapacity or substantial disruption of the ability to conduct normal life functions; or,
- A congenital anomaly/birth defect.

Important medical events that may not result in death, be life-threatening, or require hospitalization may be considered serious when, based upon appropriate medical judgment, they may jeopardize the patient and may require medical or surgical intervention to prevent one of the outcomes listed above. Examples of such medical events include allergic bronchospasm requiring intensive treatment in an emergency room or at home, blood dyscrasias or convulsions that do not result in inpatient hospitalization, or the development of drug dependency or drug abuse.

Hospitalization is defined as any inpatient overnight stay in a hospital. This does not include an emergency room visit or admission to an outpatient facility.

A hospitalization in and of itself should not be reported as an SAE.

Hospitalizations for preplanned or elective surgery or routine clinical procedures without worsening of the underlying condition, or for administrative/social reasons (such as convenience, logistics) should not be reported as SAEs. However, if an elective procedure has to be performed sooner than planned due to a worsening of the underlying medical condition and the patient is hospitalized for the procedure, the worsening medical condition should be reported as an SAE.

Any laboratory abnormality fulfilling any of the criteria for an SAE should be reported as such.

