5.5 Safety Population

The Safety population is defined as those randomized patients who take at least 1 dose of study drug during the double-blind Treatment Period. Safety patients are analyzed according to their actual treatment received on Study Day 1.

6. Data Handling

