6.1 Time Points and Visit Windows

Day 1, defined as the Baseline/Randomization visit, is also the first day that study treatment during the double-blind Treatment Period is planned to be started. Should study treatment start at a later date, Day 1 will be defined as the date that

CONFIDENTIAL

study treatment during the double-blind Treatment Period is initiated. Relative days after Day 1 are calculated as (assessment date – Day 1 date) + 1. Relative days prior to Day 1 are calculated as (assessment date – Day 1 date). The day prior to Day 1 is Day -1; there is no Day 0.

6.1.1 Primary efficacy, secondary efficacy, and other efficacy endpoints based on daily pain diary data

The following time point windows defined in [Table 1.1](#) will be used for the analyses of the primary efficacy endpoint, the secondary efficacy endpoints, and other efficacy endpoints based on the ADPS as well as for the secondary endpoint on pain interfering with sleep.

Table 1.1 Definition of time point windows for analyses based on ADPS and sleep interference rated each evening

Time point	Time point window ^a
Baseline	Day -7 to Day -1
Week 1	Days 1 to 7
Week 2	Days 8 to 14
Week 3	Days 15 to 21
Week 4	Days 22 to 28
Week 5	Days 29 to 35
Week 6	Days 36 to 42
Week 7	Days 43 to 49
Week 8	Days 50 to 56
Week 9	Days 57 to 63
Week 10	Days 64 to 70
Week 11	Days 71 to 77

^a relative to the date of first dose of study drug during the double-blind Treatment Period/ date of Randomization/date of Baseline Visit (Day 1)

The Baseline value for ADPS based on Question 5 of the ZBPI will be calculated as the mean value of the corresponding question over Week 2 of the single-blind Run-in Period, provided that ≥5 days with non-missing data from that period are available for analysis. The Baseline value for the interference with sleep using Question 9F of the ZBPI is defined as the value collected at the time of the clinic visit on Day 1 but prior to intake of the first dose of study drug. As a sensitivity analysis, the mean value of Question 9F of the ZBPI of daily diary over Week 2 of the single-blind Run-in Period will be used as the Baseline, provided that ≥5 days with non-missing data from that period are available for analysis.

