7.2 Patient Disposition and Data Sets Analyzed

Patient disposition will be listed and summarized by treatment group and overall, and will include the number and percentage of patients:

- Screened
- Entered single-blind placebo Run-in Period

CONFIDENTIAL

- Discontinued single-blind placebo Run-in Period
- Randomized
- Randomized and not treated
- Treated
- Completed double-blind Treatment Period
- Discontinued double-blind Treatment Period
- Entered optional qualitative patient interview substudy
- Completed single-blind Safety Follow-up Period
- Discontinued single-blind Safety Follow-up Period
- Included in each study population (ITT, mITT, PP, PK and Safety)

The number and percentage of patients who complete the study and who discontinue early (including a breakdown of the primary reasons for discontinuation), will be presented for the ITT population. In addition, the number of patients who discontinue from the double-blind Treatment Period and single-blind Safety Follow-up Period will be summarized, respectively.

A summary of patient enrollment by site will be provided by treatment group and overall for the ITT population. A summary of patient enrollment by randomization strata of baseline pain severity (moderate or severe pain, based on ADPS) will also be provided by treatment group, respectively.

Randomization strata will be collected in the Interactive Voice/Web Response System (IXRS) and it is defined as the average of the scores recorded in the pain diary, ie, Question 5 of the ZBPI, during the 2-week single-blind Run-in Period. The rounded average score will be classified as below:

- Moderate: [5-7]
- Severe: [8-9]

A summary of the reasons for screen failure as well as the number of patients screened but not randomized will be produced. No other information for screen failures will be presented.

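### The summary of fatal Screening and Run-in SAEs is run on the Safety population, so a patient who dies before Day 1 is excluded from it by construction

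*SAP*

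**What the plan says.** Protocol 9.1.2 opens the SAE window at consent: "All SAEs will be collected starting with signing informed consent". Note g to the schedule of events (protocol Appendix A) agrees, so fatal events before randomisation are meant to be in the database.

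SAP 7.7.2 introduces its list of AE tables with "The number and percentage of patients reporting each AE will be summarized by SOC and PT for the Safety population". One line of that list, directly after the table of fatal TEAEs, is "SAEs during Screening or Run-in Periods leading to death, by SOC and PT". No other population is named for it.

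SAP 5.5 defines the population: "The Safety population is defined as those randomized patients who take at least 1 dose of study drug during the double-blind Treatment Period". It then assigns the column: "Safety patients are analyzed according to their actual treatment received on Study Day 1". SAP 6.1 fixes the date: "Day 1, defined as the Baseline/Randomization visit, is also the first day that study treatment during the double-blind Treatment Period is planned". If dosing starts later, Day 1 moves to the first double-blind dose.

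The protocol's Safety Population (10.2.5) is wider. It requires only some exposure to study drug, and protocol 5.1.2 and 7.4 use the term study drug for the Run-in tablets.

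For patients who are not randomised, SAP 7.2 gives disposition counts, including entry to and discontinuation from the Run-in, and a summary of screen-failure reasons. It then says: "No other information for screen failures will be presented".

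**The concern.** The line has a clear purpose. Deaths from treatment-emergent events have their own table, so a separate table for fatal SAEs arising in Screening or Run-in is there to report what happens before double-blind treatment. The population attached to it removes the most obvious cases: patients who die in that period.

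At stake is how a reader of the study report interprets an empty table. Unless the population is spelled out, no entries will be taken as a statement about everyone who entered Screening or Run-in, when it describes only those who survived to be randomised and dosed.

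**Working it through.** The plan gives no figure here to reproduce, so the check is one of set membership.

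**Condition for entering the table.** A patient must satisfy all of:
1. an SAE arising in Screening or Run-in that leads to death (SAP 7.7.2);
2. randomised (SAP 5.5);
3. at least one double-blind dose (SAP 5.5).

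The first double-blind dose falls on or after Day 1 (SAP 6.1). Death before Day 1 therefore rules out condition 3, and the overlap with the Safety population is empty.

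**Case by case, under the two definitions of the Safety population:**

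| Patient | SAP 5.5 | Protocol 10.2.5 |
|---|---|---|
| Dies in Screening, no tablet taken | Out | Out |
| Dies in Run-in after a placebo tablet, not randomised | Out | Arguably in |
| Randomised, dies before any double-blind dose | Out | Arguably in |
| SAE starts before Day 1; randomised, dosed, then dies of it | In | In |

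Only the last row can be counted under the SAP. The protocol definition would recover the two middle rows if Run-in placebo counts as study drug, but not the first. Reverting to it would be only a partial repair. SAP Section 8, which records changes to the planned analysis, does not mention the narrowing.

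**Denominator and column.** SAP 7.1 takes percentages over patients per treatment group in the analysis population unless a table shell says otherwise. A patient who was never randomised has no treatment group, so has neither a denominator nor a column.

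**Length of the window.** From the duration entry in the protocol synopsis: Screening up to 2 weeks + Run-in 2 weeks = 4 weeks. Total 2 + 2 + 6 + 5 = 15 weeks, which is 15 × 7 = 105 days, as the synopsis states.

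**Other outputs in which such a death could appear:**
- SAP 7.7.2 lists all AE data with TEAE status flagged. The flag implies that non-TEAEs are included, but the listing is sorted by treatment group.
- The dedicated SAE and death listings in SAP 7.7.2 cover treatment-emergent events only.
- Protocol 10.4.5.2 promises listings of deaths and SAEs without that restriction, although protocol 10.4.5 places safety analyses on the Safety Population.
- SAP 7.2 presents reasons for early discontinuation for the ITT population, that is, randomised patients only.

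**The case against.** The strongest reply is that nothing need be lost. The SAP's all-AE listing and the protocol's listings of AEs, SAEs and deaths can carry a pre-Day 1 death. Fatal SAEs reach the sponsor within 24 hours (protocol 9.4), and the DMC receives monthly SAE summaries. A table labelled as Safety population is narrow rather than untrue. The table shells, which are not in the documents, might name another population for this line. These are pre-treatment events, so no treatment comparison is touched.

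Most of this stands as a limit on the consequence, and it defeats several stronger readings that a reader might infer:
- *That such deaths go unreported altogether.* The listings above contradict this. What remains is that the SAP does not say how listings sorted by treatment group handle patients with no group.
- *That the table must always be empty.* It is not: an SAE that starts in Run-in and proves fatal after dosing qualifies.
- *That SAP 7.2 forbids any report of a Run-in death.* The restriction follows the screen-failure summary, and Run-in discontinuations are a separate disposition category. The SAP does not call a Run-in death a screen failure, although the reference to patients screened but not randomised leaves that reading open.
- *That risk is raised in this window because patients are coming off prohibited pain treatments.* The documents place that washout before Screening, and the bar on rescue medication is stated for the Run-in only.

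None of this answers the narrow point: on the SAP's text, the one table written for these deaths cannot contain a death before Day 1.

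**Conclusion.** The point holds for this one table. Under SAP 5.5 and 7.7.2 the number of pre-Day 1 deaths it can show is zero whatever happens, for up to 4 of about 15 weeks of participation. How many patients this leaves outside the table cannot be estimated, because the documents give no expected number of screen or Run-in failures.

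The conclusion assumes that the introductory sentence in SAP 7.7.2 governs every line of its list, and that no table shell overrides it. It also assumes SAEs are collected from consent, as protocol 9.1.2 states; the opening text of protocol Section 9 is narrower for events before the first dose and should be read alongside it.

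This is a stated rule that gives the wrong count for the table's evident purpose, rather than a missing detail. It should be corrected because doing so costs almost nothing. It bears on the completeness of descriptive safety reporting only, and not on the primary analysis, power, Type I error or the between-group safety comparison.

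**What to change.** 1. In SAP 7.7.2, name the population for this summary as all patients who signed consent, with one overall column and no treatment columns.
2. State in SAP 7.7.2 that the listing of all AE data includes non-randomised patients under a not-randomised heading, and amend the screen-failure sentence in SAP 7.2 to permit it. No additional listing is then needed.
3. Reconcile the Safety population in SAP 5.5 with protocol 10.2.5. If the SAP's narrower definition is kept for the treatment-group tables, record the change in SAP Section 8.

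The cost is one population label, one listing heading and a few sentences. Protocol 9.1.2 already requires the data to be collected.

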7.7.3 Laboratory Evaluations

Data for the following hematology, serum chemistry, lipid panel, and urinalysis analytes received from central laboratory will be listed and summarized by treatment group and visit. If data for any additional analytes are also received, then these will be listed only.

Hematology	Serum Chemistry	Urinalysis
Complete blood count (CBC) with differential Platelet count	Albumin Alkaline phosphatase Alanine transaminase (ALT) Amylase Aspartate transaminase (AST) Total bilirubin Glucose Blood urea nitrogen (BUN) Calcium Carbon dioxide Chloride Creatinine Magnesium Phosphorus Potassium Sodium Total protein Uric acid	Appearance Color Glucose Ketones Nitrite pH Protein Specific gravity Occult blood Leukocyte esterase Bilirubin Urobilinogen Urine microscopy White blood cell Red blood cell Epithelial cells Bacteria Casts Crystals
Lipid panel	Other Samples	
High-density lipoprotein (HDL) Low-density lipoprotein (LDL) Total cholesterol Triglycerides Creatinine phosphokinase (CPK)	Pregnancy tests (females only) Urine screen (drugs of abuse and THC)	

All laboratory data will be reported in International System of Units and conventional units. Out-of-reference-range values will be flagged as high (H) or low (L) in the listings.

For analysis purposes, values preceded by a "<" or a ">" sign (ie, those below or above the limits of quantification) will be considered equal to the lower or upper limit of quantification, respectively.

Laboratory data will be summarized by visit using standard descriptive statistics by treatment group and overall for the Safety population. Changes from Baseline will also be summarized.

For hematology and serum chemistry, shift tables presenting movement in and out of reference range from Baseline to each scheduled post-Baseline visit will be provided by treatment group and overall for the Safety population. Percentages will be based on the number of patients with both non-missing Baseline and relevant post-Baseline results.

For each laboratory analyte, the Baseline value will be defined as last scheduled or unscheduled value collected prior to the first dose of study drug during the double-blind Treatment Period. Assessments carried out on the day of first study drug administration are considered to have taken place before the study drug administration, if the corresponding times have not been recorded.

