8.1.3 Clinical Laboratory Assessments

Clinical laboratory assessments will include, at a minimum, blood chemistry (albumin, alkaline phosphatase, alanine transaminase [ALT], amylase, aspartate transaminase [AST], total bilirubin, glucose, blood urea nitrogen [BUN], calcium, carbon dioxide, chloride, creatinine, magnesium, phosphorus, potassium, sodium, total protein, and uric acid), lipid panel (high-density lipoprotein (HDL), low-density lipoprotein (LDL), total cholesterol, triglycerides, creatinine phosphokinase [CPK]), hematology (complete blood count [CBC] with differential, and platelet counts), and urinalysis (including appearance, color, glucose, ketones, nitrite, pH, protein, specific gravity, occult blood, leukocyte esterase, bilirubin, and urobilinogen). Urine microscopy will only be performed if any of the following are present in the urine sample: occult blood, leukocyte esterase, protein, or nitrite. The microscopy will include analysis for the presence of WBC, red blood cells, epithelial cells, bacteria, casts, and crystals.

Additional assessments such as: pregnancy tests [females only]), and a urine screen (drugs of abuse and THC) will be done at time points specified in [Appendix A](#).

The incidence of clinically significant laboratory values, as well as clinically significant shifts in laboratory values, should be reported as an AE ([Section 9.1.1](#)) and followed as described in [Section 9.5](#); retests should be performed as frequently as clinically indicated.

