| Patient completes HADS | X | | | | | | |
| Seated vital signs | X | | X | X | X | X | X |
| Orthostatic vitals [d] | | | X | | | | |
| 12-lead ECG [e] | X | | X | | | X | X |
| Assess dose compliance | | | X | X | X | X | X |

| Week/Visit Window (days) | Screening Period (up to 2 Weeks) | Single-blind Placebo Run-in Period | Double-blind Treatment Period | | | | Single-Blind Safety Follow-up Period |
|---|-------------------------------------|--|-------------------------------|---------|---------|--------------------------|---|
| | Visit 1 | Visit 2 | Visit 3 | Visit 4 | Visit 5 | Visit 6 | Visit 7 |
| | Week -4 | Week -2 | Day 1 (Baseline) [a] | Week 2 | Week 4 | Week 6 Or EOT / EW | Week 11[b] Or 35 days after EOT / EW |
| | | | +3 | ±3 | ±3 | ±3 | ±5 |
| Record concomitant medications [f] | X | X | X | X | X | X | |
| Record SAEs [g] | X | X | X | X | X | X | X |
| Record AEs [h] | | X | X | X | X | X | X |
| Dispense single-blind placebo | | X | | | | X | |
| Dispense double-blind study drug | | | X | X | X | | |
| Patient-reported Outcome | | | | | | | |
| Dispense patient daily e-diary | | X | | | | | |
| Patient completes Question 5 of ZBPI and other ePRO questions on e-diary | |  | | | | | |
| Review patient daily e-diary | | | X | X | X | X | X |
| Patient completes the Zoster Brief Pain-Inventory (ZBPI), dispense/review | | | X | X | X | X | X |
| Patient completes PGIC | | | | | | X | X |
| Patient completes NPSI | | | X | | | X | X |
| Laboratory Assessments | | | | | | | |
| Serum chemistry | X | | X | X | X | X | X |
| Hematology | X | | X | | | X | X |
| Urinalysis with microscopy | X | | X | X | X | X | X |
| Pregnancy test (serum) [i] | X | | | | | | |
| Pregnancy test (urine) [i] | X | | X | | | X | |
| FSH (females only) [j] | X | | | | | | |
| Urine drug test for drugs of abuse and cannabinoids | X | | X | | | | |

| | | | | | | | |
|---|--|--|----------------------------|---|---|---|---|
| C _{p2hr} and C _{trough} blood samples [k] | | | X (pre- and 2-hr postdose) | X | X | X | X |
| | | | | | | | |
| Exit Interview Substudy Assessments | | | | | | | |
| Exit interview [l] | | | | | | X | |

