6.2 Handling of Dropouts, Missing Data, and Outliers

Missing data will not be imputed for safety analyses. The safety evaluations will be performed on observed data only.

For AEs with partial or missing onset or stop dates:

AE stop date will be imputed first as:

- If stop date is completely missing, assume it is ongoing (no imputation)
- For a partial AE stop date:
 - day is missing, then take the last day of the month
 - both day and month are missing, then take last day of the last month that the patient was on study

Then AE onset date will be imputed as:

- If onset date is completely missing: the first dose date
- For a partial AE onset date:
 - day is missing:
 - Partial date < the first dose date: last day of the month
 - Partial date = the first dose date: the first dose date
 - Partial date > the first dose date: first day of the month
 - both day and month are missing ie, only the year is available:
 - Partial date < the first dose date: December 31st
 - Partial date = the first dose date: the first dose date
 - Partial date > the first dose date: January 1st

If the imputed AE onset date is after the AE stop date/imputed AE stop date, then the onset date will be set to the AE stop date/imputed AE stop date.

The imputed dates will not be listed. Study day relative to the first dose of double-blind study drug associated with missing or partial dates will not be displayed in AE listings.

In the event that a partial date (month/year or year) for concomitant medication is available, this information will be used as follows:

- When both month and year are available – first day of the month will be used for start date and the last day of the month will be used for the stop date.
- When only year is available – January 1st will be used for the start date and December 31st will be used for the stop date.

The imputed dates will only be used to determine whether a concomitant medication will be classified as prior medication or concomitant medication.

For patients who complete the NPSI assessment, but have 1 incomplete answered question, the total score will be computed as 10 times sum of scores of 9 descriptors divided by 9. If more than 1 question is missing, then the total score will be missing. Missing questions will not be imputed for the subscores.

The Hospital Anxiety and Depression Scale (HADS) is collected only at Screening and imputation of missing data is not critical for this assessment.

No rules for outlier detection are planned.

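### SAP 7.7.3 summarises reflex-only urine microscopy, and its change from Baseline, with no rule for untriggered tests, so a patient with no pre-dose trigger who develops urinary red or white cells has no change value

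*SAP*

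**What the plan says.** Protocol 8.1.3 makes microscopy conditional: "Urine microscopy will only be performed if any of the following are present in the urine sample: occult blood, leukocyte esterase, protein, or nitrite". The schedule of events (Protocol Appendix A, repeated in SAP Appendix 2) has a row headed "Urinalysis with microscopy", marked at Screening, Day 1 and Weeks 2, 4, 6 and 11, with no condition attached.

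SAP 7.7.3 puts microscopy white cells, red cells, epithelial cells, bacteria, casts and crystals in the urinalysis column of its analyte table. The sentence that introduces that table states that "urinalysis analytes received from central laboratory will be listed and summarized by treatment group and visit". The section then applies general rules to all laboratory data:

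- By-visit summaries: "Laboratory data will be summarized by visit using standard descriptive statistics by treatment group and overall for the Safety population".
- Change scores, with no exception made for microscopy: "Changes from Baseline will also be summarized".
- Baseline, defined separately per analyte: "the Baseline value will be defined as last scheduled or unscheduled value collected prior to the first dose of study drug" in the double-blind period.

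SAP 6.2 adds "Missing data will not be imputed for safety analyses". SAP 7.7.3 provides shift tables for hematology and serum chemistry only. Protocol 10.4.5.3 describes shift tables for laboratory results without that restriction.

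**The concern.** A change from Baseline needs a pre-dose and a post-dose value. For microscopy, each value exists only if the dipstick triggered the test. Whether the value is missing therefore depends on the finding itself: a clean dipstick is informative, but the SAP handles the absent microscopy as no data.

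Two consequences follow. A patient with no pre-dose trigger who develops red or white cells on treatment cannot enter the microscopy change summary. And any numeric by-visit summary describes triggered samples only, so it need not move when more patients become positive.

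This matters more here than in most trials. Protocol 9.1.1.1 reports urinary bladder changes in dogs and commits to close monitoring of bladder-related adverse events. A change table for urinary cells that cannot show new onset in most of the relevant patients gives little information on that organ, and it can mislead if read alone.

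**Working it through.** The plan states no figure on this point, so there is nothing to reproduce. The check is of logic, followed by an illustration on assumed rates.

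**Logic**

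1. Microscopy is done only if a trigger is present (Protocol 8.1.3).
2. Baseline is the last pre-dose value of that analyte (SAP 7.7.3). With no pre-dose trigger there is no microscopy Baseline.
3. Nothing is imputed (SAP 6.2), so a later positive result has no change value.
4. SAP shift tables exclude urinalysis. Their percentages also use only patients with a non-missing Baseline and post-Baseline result, so extending them unchanged would still omit this patient.

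**How many patients the change table would hold**

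Inputs: 37 patients per arm and 15% dropout (Protocol 10.1), so n = 37 × 0.85 = 31.45, about 31.5. The trigger rate p per sample is assumed to be 10%, 20% or 30%, because the documents give none. Screening and Day 1 both carry a urinalysis, and either can supply a Baseline.

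- Independent samples: n × p × [1 − (1 − p)²]
  - p = 0.10: 31.45 × 0.10 × 0.19 = 0.6
  - p = 0.20: 31.45 × 0.20 × 0.36 = 2.3
  - p = 0.30: 31.45 × 0.30 × 0.51 = 4.8
- Fully persistent positivity: n × p = 3.1, 6.3 and 9.4, or about 3, 6 and 9.

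**How many new cases lack a Baseline**

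Take a patient with new haematuria or pyuria to be negative for blood and leukocyte esterase before dosing. A microscopy Baseline then exists only if protein or nitrite triggered the test. Let that chance be q per pre-dose sample, assumed to lie between 5% and 30%.

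- One pre-dose sample: 1 − q = 95% to 70% have no Baseline.
- Two independent samples: (1 − q)² = 90% to 49% have no Baseline.

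**Direction of the error, constructed example**

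In an arm of 37, suppose 30 patients stay at 0 red cells, 5 go from 0 to 20, and 2 go from 10 to 8. Only the last 2 had a pre-dose trigger.

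- All patients tested: (5 × 20 + 2 × (−2)) / 37 = 96/37 = +2.6.
- As the plan is written: mean of the 2 paired patients = −2.0.

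The sign is reversed. This shows that reversal is possible, not that it is expected.

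**The case against.** The strongest reply is that these patients are not hidden, and most of it stands.

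- **New cases appear elsewhere.** The four triggers are themselves urinalysis analytes in SAP 7.7.3 and are summarised by visit. Listings flag out-of-range values. Clinically significant laboratory values and shifts are to be reported as adverse events (Protocol 8.1.3). A reader might infer that new haematuria or pyuria drops out of safety reporting. The documents do not support that; the loss is confined to the change summary.
- **The SAP does not say that it averages microscopy.** SAP 7.1 gives means for continuous variables and counts for categorical ones, and the table shells are not available. If results are categorical, the default denominator is all patients in the group, with a Missing row. That reduces the problem, but it still mixes tests not triggered with data truly missing.
- **The number tested is visible.** If trigger rates doubled from 20% to 40%, a numeric table could show the same mean, but its n would go from about 6 to about 13 (31.45 × 0.20 and 31.45 × 0.40).
- **Some new cases do have a Baseline.** A reader might infer that the change table contains no newly positive patient. That is too strong: a pre-dose protein or nitrite trigger, a positive Screening sample or an unscheduled test can each supply one.
- **The schedules read as unconditional.** If microscopy were run on every sample, the problem would disappear. The two statements conflict, and Protocol 8.1.3 is the explicit one.

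What survives is a stated summary whose missingness depends on the outcome, with no shift table to compensate.

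**Conclusion.** The point holds as a minor one. As written, a patient with no pre-dose trigger who develops urinary red or white cells has no microscopy change value, and no planned shift table counts the new onset. Numeric by-visit summaries, where used, describe triggered samples only.

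The change table would probably be nearly empty if samples are independent, and would still hold under a third of the arm with full persistence at a 30% trigger rate (9.4 of 31.45). These sizes rest on assumed trigger rates, equal before and after dosing, and on Protocol 8.1.3 being what sites and the laboratory follow. The safety tables are descriptive with no significance tests (Protocol 10.4.5), so neither the primary analysis nor any other efficacy result is affected.

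**What to change.** In SAP 7.7.3:

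1. Replace means and mean changes for microscopy with the number and percentage abnormal at each visit, among all patients with a urinalysis at that visit.
2. Show not triggered as its own category, separate from missing. Do not code it as negative: that would assign a result to a test not done and would sit badly with the no-imputation rule in SAP 6.2.
3. Extend the shift tables to the dipstick items and microscopy, with not triggered as a Baseline level, so that newly abnormal patients are counted. This also brings the SAP closer to Protocol 10.4.5.3.

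Separately, reconcile the microscopy row in both schedules with Protocol 8.1.3.

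The cost is SAP wording and table programming. No new data are needed.
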